3.8.1 Adverse events (AEs)

For reporting of AEs the overall observation period will be divided into mutually exclusive categories, including pre-treatment, on-treatment, post-treatment periods as defined in [Section 2.1.1](#).

[figure not shown]
AE summaries will include all AEs occurring (new or worsening) during on-treatment period. All AEs collected in the AE eCRF page will be listed along with the information collected on those AEs e.g. AE relationship to study drug, AE outcome etc. AEs with start date outside of on-treatment period will be flagged in the listings.

AEs will be summarized by number and percentage of patients having at least one AE, having at least one AE in each primary system organ class (SOC) and for each preferred term (PT) using MedDRA coding. A patient with multiple occurrences of an AE will be counted only once in the respective AE category. A patient with multiple CTCAE grades for the same preferred term will be summarized under the maximum CTCAE grade recorded for the event. AE with missing CTCAE grade will be included in the ‘All grades’ column of the summary tables.

In AE summaries, the primary system organ class will be presented alphabetically and the preferred terms will be sorted within primary SOC in descending frequency. The sort order for the preferred term will be based on the descending frequency in all patients.

The following adverse event summaries will be produced by group; overview of adverse events and deaths, AEs by SOC and PT, summarized by relationship (all AEs and AEs related to study treatment), seriousness (SAEs and non-SAEs), leading to treatment discontinuation, leading to dose interruption/adjustment, and leading to fatal outcome.

3.8.1.1 Adverse events of special interest / grouping of AEs

[REDACTED]

For each AESI, number and percentage of patients with at least one event of the AESI occurring during on-treatment period will be summarized. Summaries of AESIs will be provided by group (specifying grade, SAE, relationship, leading to treatment discontinuation, leading to dose adjustment/interruption, hospitalization, death etc.).

A listing of all grouping levels down to the MedDRA preferred terms used to define each AESI will be generated.

In addition to summarizing infections by CTCAE grade, they will also be summarized using infection severity (protocol Appendix 1) for the on-treatment period. A listing of infection with infection severity will be generated and the events with start date outside of on-treatment period will be flagged.

3.8.1.2 Adverse events of clinical trial safety disclosure

For the legal requirements of ClinicalTrials.gov and EudraCT, two required tables on adverse events which are not serious adverse events with an incidence greater than 5% and on serious adverse events and SAE suspected to be related to study treatment will be provided by system organ class and preferred term on the safety set population.

If for a same patient, several consecutive AEs (irrespective of study treatment causality, seriousness and severity) occurred with the same SOC and PT:

- a single occurrence will be counted if there is ≤ 1 day gap between the end date of the preceding AE and the start date of the consecutive AE
- more than one occurrence will be counted if there is > 1 day gap between the end date of the preceding AE and the start date of the consecutive AE

For occurrence, the presence of at least one SAE / SAE suspected to be related to study treatment / non SAE has to be checked in a block e.g., among AE's in a ≤ 1 day gap block, if at least one SAE is occurring, then one occurrence is calculated for that SAE.

The number of deaths resulting from SAEs suspected to be related to study treatment and SAEs irrespective of study treatment relationship will be provided by SOC and PT.

3.8.2 Deaths

Separate summaries for on-treatment and all deaths (including post-treatment death) will be produced by age group, system organ class and preferred term.

All deaths will be listed and deaths that occurred outside of on-treatment period will be flagged. A separate listing of deaths prior to starting treatment will be provided for all screened patients.

3.8.3 Laboratory data

Laboratory, data from all sources (central and local laboratories) will be combined.

Grading of laboratory values will be assigned programmatically as per NCI Common Terminology Criteria for Adverse Events (CTCAE) version 4.03. The calculation of CTCAE grades will be based on the observed laboratory values only, clinical assessments will not be taken into account.

CTCAE Grade 0 will be assigned for all non-missing values not graded as 1 or higher.

For laboratory tests where grades are not defined by CTCAE v4.03, results will be categorized as low/normal/high based on laboratory normal ranges.

The following summaries will be produced for hematology and biochemistry laboratory data (by laboratory parameter and group):

- Shift tables using CTC grades to compare baseline to the worst on-treatment value
- For laboratory tests where CTC grades are not defined, shift tables using the low/normal/high/(low and high) classification to compare baseline to the worst on-treatment value.

The following listings will be produced for the laboratory data:

- Listings of all laboratory data, with CTC grades and classification relative to the laboratory normal range. Lab data collected during the post-treatment period will be flagged.
- Listing of all CTC grade 3 or 4 laboratory toxicities

The results from viral load testing will be listed.

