Study treatment	Any drug administered to the study patients as part of the required study procedures; includes investigational drug (s), control(s) or non-investigational medicinal product(s)
Study treatment discontinuation	When the subject permanently stops taking study treatment prior to the defined study treatment completion date
Subject	An individual who has consented to participate in this study (or has been consented by a legal representative).
Subject number	A number assigned to each subject who enrolls in the study. When combined with the center number, a unique identifier is created for each subject in the study.
Treatment Arm/Group	A treatment arm/group defines the dose and regimen or the combination and may consist of 1 or more cohorts.
Variable	Information used in the data analysis; derived directly or indirectly from data collected using specified assessments at specified timepoints.
Withdrawal of consent (WoC)/Opposition to use data/biological samples	Withdrawal of consent from the study occurs when the patient explicitly requests to stop use of their data and biological samples (opposition to use data and biological samples) AND no longer wishes to receive study treatment AND does not agree to further required assessments. This request should be in writing (depending on local regulations) and recorded in the source documentation. Opposition to use data/biological samples occurs in the countries where collection and processing of personal data is justified by a different legal reason than consent.

Amendment 3

Amendment rationale

As of 11Feb2021, CINC424F12201 completed enrollment with a total of 45 patients, which included 29% treatment-naïve patients and 71% SR-aGvHD patients. Treatment by Group consisted of 18 patients in Group 1 (age ≥ 12 y to < 18 y), 12 patients in Group 2 (age ≥ 6 y to < 12 y) and 15 patients in Group 3 (age ≥ 2 y to < 6 y).

The main purpose of this amendment to include public health emergency disruption proofing language, to provide guidance on patient management, including withdrawal of consent, and to decrease the minimum enrollment requirement of treatment-naïve patients from 40% to at least 20% due to recruitment challenges. The sample remains representative of the study population and therefore the sample size was not re-estimated due to this modification.

Changes to the protocol

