7. Phase II To measure the activity of ruxolitinib in patients with aGvHD or SR-aGvHD assessed by Overall Response Rate (ORR) at Day 28.	8. Overall response rate (ORR) at Day 28, defined as the proportion of patients demonstrating a complete response (CR) or partial response (PR) without requirement for additional systemic therapies for an earlier progression, mixed response or non-response. Scoring of response will be relative to the organ stage at the start of the study treatment.
Secondary objective(s)	Endpoint(s) for secondary objective(s)
9. Key Secondary To assess the rate of durable ORR at Day 56	10. Proportion of all patients who achieve a CR or PR at Day 28 and maintain a CR or PR at Day 56
11. To estimate ORR at Day 14	12. Proportion of patients who achieved OR (CR+PR) at Day 14
13. To assess pharmacokinetic/pharmacodynamic relationships	14. PK parameters (such as AUC, Cmax, Ctrough) versus safety, efficacy, and PD biomarkers, as appropriate
15. To assess Duration of response	16. Duration of response (DOR) is assessed for responders only and is defined as the time from first response until aGvHD progression or the date of additional systemic therapies for aGvHD. Onset of chronic GvHD, or death without prior observation of aGvHD progression are considered as competing risks
17. To assess the cumulative steroid dose until Day 56	18. Weekly cumulative steroid dose for each patient up to Day 56

Objective(s)	Endpoint(s)
19. To evaluate the safety and tolerability of ruxolitinib	20. Safety and tolerability including myelosuppression, infections, and bleeding will be assessed by monitoring the frequency, duration and severity of Adverse Events including occurrence of any second primary malignancies, infections, by performing physical exams, and evaluating changes in vital signs from baseline, routine serum chemistry, hematology results and coagulation profile
21. To assess Overall Survival (OS)	22. Overall survival, defined as the time from the start of treatment to the date of death due to any cause
23. To assess Event-Free Survival (EFS)	24. Event-free survival, defined as the time from start of treatment to the date of hematologic disease relapse/progression, graft failure, or death due to any cause
25. To assess Failure-Free Survival (FFS)	26. Failure-free survival, defined as the time from the start of treatment to date of hematologic disease relapse/progression, non-relapse mortality, or addition of new systemic aGvHD treatment

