8.5.4 Laboratory evaluations

Table 8-4 Local clinical laboratory parameters collection plan

Test Category	Test Name
Hematology	Hematocrit, Hemoglobin, Mean Corpuscular Hemoglobin (MCH), Mean Corpuscular Hemoglobin Concentration (MCHC), Mean Corpuscular Volume (MCV), Platelets, Red blood cells (RBC), White blood cells (WBC). RBC Morphology, Differential (Basophils, Eosinophils, Lymphocytes, Monocytes, Neutrophils, Absolute Neutrophil Count (ANC), Absolute Reticulocytes, Bands

Test Category	Test Name
Chemistry	Albumin, Alkaline phosphatase, ALT (SGPT), AST (SGOT), Gamma glutamyl transferase (GGT), Lactate Dehydrogenase (LDH), Bicarbonate, Calcium, Creatinine, Magnesium, Phosphorus, Chloride, Sodium, Potassium, Total Bilirubin, Direct Bilirubin, (Indirect Bilirubin only if Total Bilirubin out of range), Blood Urea Nitrogen (BUN) or Urea, Creatine kinase, Total Cholesterol, Low Density Lipoprotein (LDL), High Density Lipoprotein (HDL), Total Protein, Triglycerides, Uric Acid, Amylase, Lipase, Glucose
Urinalysis	Macroscopic Panel (Dipstick)* (Color, Bilirubin, Blood, Glucose, Ketones, Leukocytes esterase, Nitrite, pH, Protein, Specific Gravity, Urobilinogen) *Note: Any findings on dipstick will be followed up with a microscopic evaluation (Red Blood Cells, White Blood Cells, Casts, Crystals, Bacteria, Epithelial cells)
Coagulation	Prothrombin time (PT), International normalized ratio (INR), Partial thromboplastin time (PTT) or Activated partial thromboplastin time (APTT), D-Dimer, Fibrinogen
Hepatitis markers	Hepatitis B surface antigen, Hepatitis B surface antigen antibody, Hepatitis B core antibody (baseline) and HBV DNA-PCR (baseline and during treatment period) Hepatitis C virus antibody (baseline) and HCV RNA-PCR (baseline and during treatment period) Note: Prior HBV and HCV serology test results obtained as part of standard of care prior to alloSCT (i.e., hepatitis B or C surface antigen negative, surface antibody positive) may be used. Baseline serology tests do not need to be repeated during the Screening period
Additional viral testing as applicable	Cytomegalovirus (CMV), Epstein Barr Virus (EBV), Human Herpes Virus (HHV-6), Herpes Simplex Virus (HSV), Varicella Zoster Virus (VZV) and Adenovirus (ADV) viral load
Pregnancy Test	Serum at Screening, End of Treatment (EOT) and Safety follow-up Urine at all other time points Per Investigator discretion, a serum pregnancy test can be performed in lieu of a urine pregnancy test.

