10.1 Definition of adverse events and reporting requirements

10.1.1 Adverse events

An adverse event is defined as the appearance of (or worsening of any pre-existing) undesirable sign(s), symptom(s), or medical condition(s) that occur after patient’s signed informed consent has been obtained.

Abnormal laboratory values or test results occurring after informed consent constitute adverse events only if they induce clinical signs or symptoms, are considered clinically significant, require therapy (e.g., hematologic abnormality that requires transfusion or hematological stem cell support), or require changes in study medication(s).

Adverse events that begin or worsen after informed consent should be recorded in the Adverse Events eCRF. Conditions that were already present at the time of informed consent should be recorded in the Medical History page of the patient’s eCRF. Adverse event monitoring should be continued for at least 30 days following the last dose of study treatment. Adverse events (including lab abnormalities that constitute AEs) should be described using a diagnosis whenever possible, rather than individual underlying signs and symptoms. When a clear diagnosis cannot be identified, each sign or symptom should be reported as a separate Adverse Event.

Adverse events will be assessed and graded according to the Common Terminology Criteria for Adverse Events (CTCAE) version 4.03.

If CTCAE grading does not exist for an adverse event, the severity of mild, moderate, severe, and life-threatening, death related to the AE corresponding respectively to Grades 1 - 5, will be used. Information about any deaths (related to an Adverse Event or not) will also be collected through a Death form.

The occurrence of adverse events should be sought by non-directive questioning of the patient (subject) during the screening process after signing informed consent and at each visit during the study. Adverse events also may be detected when they are volunteered by the patient (subject) during the screening process or between visits, or through physical examination, laboratory test, or other assessments. As far as possible, each adverse event should be evaluated to determine:

1. The severity grade (CTCAE Grade 1-5)
2. Its duration (Start and end dates)
3. Its relationship to the study treatment (related / not related)

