The proportion of patients developing Grade 2 to 3 infections using infection severity ([Section 16.1](#) Appendix 1) during the aGvHD treatment period Day 1 to Day 56 will be summarized in addition to standard CTCAE grading. In addition, proportion of patients developing second primary malignancies will be summarized based on the entire study period. A subject with multiple adverse events within a primary system organ class is only counted once towards the total of the primary system organ class.

Vital signs

All vital signs data will be listed by group, patient, and visit/time and if ranges are available, abnormalities will be flagged. Summary statistics will be provided by group and visit/time.

Clinical laboratory evaluations

All laboratory data will be listed by group, patient, and visit/time and if normal ranges are available abnormalities will be flagged. Shift tables using the low/normal/high/ (low and high) classification will be used to compare baseline to the worst on-treatment value.

Tolerability

The number and percentage of patients who have a dose increase, reduction, or interruption will be summarized.

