Sample size	Minimum No. of responders	Response Rate	Probability to have a 90% CI with lower limit $\geq 60\%$	90% CI	
37	28	0.76	0.809	0.614	0.867
38	29	0.76	0.784	0.623	0.871
39	29	0.74	0.859	0.604	0.854
40	30	0.75	0.839	0.613	0.858
41	31	0.76	0.818	0.621	0.861
42	31	0.74	0.882	0.604	0.846
43	32	0.74	0.864	0.612	0.849
44	33	0.75	0.846	0.620	0.853
45	33	0.73	0.901	0.604	0.838
46	34	0.74	0.886	0.612	0.842
47	35	0.74	0.869	0.619	0.846
48	35	0.73	0.916	0.604	0.832
49	36	0.73	0.903	0.612	0.835
50	37	0.74	0.889	0.619	0.838

5 Change to protocol specified analyses

No change from protocol

6 Appendix

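### SAP 3.8.3 tabulates baseline-to-worst shifts for hematology and biochemistry only, so the coagulation profile named in the safety endpoint is listed but not summarised

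*SAP*

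**What the plan says.** Protocol Table 2-1 defines the laboratory part of the safety endpoint as changes in "routine serum chemistry, hematology results and coagulation profile", and SAP Table 2-3 repeats it. Protocol Table 8-4 gives coagulation its own row, apart from hematology and chemistry: "Prothrombin time (PT), International normalized ratio (INR), Partial thromboplastin time (PTT) or Activated partial thromboplastin time (APTT), D-Dimer, Fibrinogen". Protocol 8.5.4.4 schedules these tests at screening and at treatment-period visits through end of treatment.

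For analysis, the laboratory part of Protocol 12.5.2 first says that every laboratory result will be listed. It then says that shift tables on a low/normal/high classification "will be used to compare baseline to the worst on-treatment value". Neither sentence restricts the panels.

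SAP 3.8.3 introduces its shift tables with "The following summaries will be produced for hematology and biochemistry laboratory data (by laboratory parameter and group". Its listings are wider: one covers all laboratory results with grade and normal-range class, and another is a "Listing of all CTC grade 3 or 4 laboratory toxicities". SAP section 5, where departures from the protocol belong, reads "No change from protocol".

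**The concern.** Two of the three laboratory components named in the endpoint get a planned aggregate summary and the third does not. The narrower scope appears in the SAP, gives no reason and is not declared as a change.

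The trial has a single arm, so change from the patient's own baseline is the only comparison available within it for laboratory tests, and the shift table is the planned way to show that change. Protocol 8.5.4.5 gives coagulopathy, together with low platelets, as a reason for close bleeding surveillance. Platelets are in the hematology shift tables; the clotting tests would be in none.

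Adverse event tables do not fully close the gap. Under Protocol 10.1.1, abnormal laboratory results "constitute adverse events only if they induce clinical signs or symptoms, are considered clinically significant", or need therapy or a change in study medication. A coagulation shift below that threshold would be visible only by reading patient-level listings, whereas a similar shift in a chemistry or hematology test would be counted in a table. What is at stake is completeness of safety reporting, and nothing beyond that.

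**Working it through.** The plan gives no figure to reproduce here. The check compares the scope of each laboratory panel across the two documents, then counts what is left out.

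**Scope by panel**

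| Panel (Protocol Table 8-4) | Named in the endpoint | Shift table, Protocol 12.5.2 | Shift table, SAP 3.8.3 | Listing, SAP 3.8.3 |
|---|---|---|---|---|
| Hematology | yes | yes | yes | yes |
| Chemistry | yes | yes | yes | yes |
| Coagulation | yes | not excluded | no | yes |

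**Could coagulation fall under hematology?** No. The endpoint text, the assessment schedule (Table 8-1), Table 8-4 and the separate sections 8.5.4.1 and 8.5.4.4 all keep the two apart.

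**Is a coagulation table promised elsewhere in the SAP?** Section 3.1.1 sets visit windows for safety data, laboratory tests included, and section 6.3 gives general grading rules. Neither specifies a coagulation table. The SAP's amendment summaries do not mention the restriction.

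**Can the table be made from data already collected?** Yes. The tests are taken at screening and through the treatment period, so both the baseline and the worst on-treatment value should exist for most patients.

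**Upper bound on untabulated pairs.** The Amendment 3 rationale gives 45 enrolled patients: "Treatment by Group consisted of 18 patients in Group 1", 12 in Group 2 and 15 in Group 3. Table 8-4 lists five coagulation tests, taking PTT and aPTT as alternatives.

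- Group 1: 18 × 5 = 90
- Group 2: 12 × 5 = 60
- Group 3: 15 × 5 = 75
- Total: 90 + 60 + 75 = 225 = 45 × 5

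If PT and INR are treated as one test because INR is derived from PT, the total is 45 × 4 = 180. Missing baseline or on-treatment values lower either number.

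**The case against.** The best reply is that the departure from the protocol is inferred. In Protocol 12.5.2 the reference to every laboratory result belongs to the listing sentence, which the SAP honours in full. The shift-table sentence names no panel, so the SAP may simply be filling in a silent sentence, and section 5 would then not be wrong. The argument from silence would also sweep in urinalysis, which the endpoint does not name. Being named in the endpoint does not guarantee a table either: physical examination is named there too, yet Table 8-1 keeps it in source documents only. Finally, in 45 patients the listings can be read through, and 225 is a cell count.

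Part of this stands. The shift-table sentence does not mention coagulation, and the case for coverage rests on the absence of a limit read together with the endpoint. The count says nothing about bias or lost precision. Urinalysis, hepatitis markers and pregnancy tests are outside this point because the endpoint does not name them.

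The gap remains even if Protocol 12.5.2 is read as ambiguous. SAP Table 2-3 itself names change in the coagulation profile, and the SAP's methods give it no aggregate summary while giving one to the two components named beside it. The comparison with physical examination is weak, because those findings are not captured as database results, whereas coagulation values are numeric, collected and graded or classified in the listings.

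**Conclusion.** The concern holds, as a minor point. SAP 3.8.3 leaves one named laboratory component of the safety endpoint without the baseline-to-worst table that the other two receive, and SAP section 5 does not disclose it.

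The size is at most 225 patient-by-test pairs, assuming all 45 patients have a baseline and at least one on-treatment value for each of the five tests. Coagulation is not unreported. The values, grades and range classes are listed, severe values are listed separately, and clinically significant abnormalities and bleeding are handled as adverse events. The definition of adverse events of special interest is redacted, so nothing is assumed about it. The ruxolitinib dose rules for bleeding risk use platelet counts, which are already tabulated. The primary and key secondary analyses do not change.

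**What to change.** In SAP 3.8.3, extend the scope of the shift tables to hematology, biochemistry and coagulation. Keep the rule already stated in that section: CTCAE v4.03 grades where they are defined and low/normal/high otherwise, baseline against worst on-treatment value, by parameter and group.

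The cost is one phrase in the SAP and one more run of an existing table program on data already collected. If listings alone are really intended for coagulation, SAP section 5 should say so as a change from Protocol 12.5.2. That would make the documents consistent but would still leave the component without a summary, so adding the table is the better course.
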